### **Power and Sample Size**

Based on our cross-sectional data demonstrating a prevalence of between 4 and 8% for the primary outcome, we conservatively estimate that the prevalence of this outcome in the control group, which, because of our exclusion criteria, will be 0% at baseline, will be 5% at the Month 6 assessment. The sample size is based on the ability to detect an absolute increase of 10% for ACP for the treatment group over the control group at Month 6, consistent with effect sizes in previous TTM-tailored interventions and a judgment regarding a minimum clinically significant effect size. Sample size calculations assumed one-tailed significance testing at alpha = .05 and were based on a one-way analysis of variance for proportions with arcsine transformation and nested random effects for sites to accommodate the cluster-randomized design. Based on an enrollment of 16 sites for the study (8 matched pairs), to achieve power of .80 for the primary outcome, a final sample size of 50 individuals per site is needed, resulting in a final study sample size of 800. Assuming 20% loss to follow-up, a baseline sample size of 1000 is required.

This sample size will also be sufficient for conducting process-to-outcome analyses assessing the effects of potential mediators and moderators of outcomes using multiple regression or structural equation modeling analyses. For example, for structural models of reasonable size (e.g., df = 40–50), and assuming a close fit criterion (RMSEA = .05), power is at least .80 for groups of about 240.

### **Analysis**

The analysis is based on the study design of two groups (intervention, control) X four occasions (baseline, 2, 4, 6 months) with sites nested in groups based on cluster randomization of matched pairs of sites. Baseline analyses will include examination of group differences to evaluate the success of the matched-pairs randomization procedure and examination of potential covariates to reduce the expected within-groups dependency resulting from cluster randomization.

### **Primary Outcome**

The main outcome hypothesis is that the proportion in Action/Maintenance for the four ACP behaviors is intervention group > control group at the final 6-month assessment. Several analytical approaches are available within a more general framework of random effects

modeling incorporating both time and site level effects in addition to potentially important covariates. The basic analytical approach will employ the generalized estimating equation (GEE) method to analyze intervention main effects and interaction (additive) effects. GEE enables use of linear, logistic and Poisson regression methods with repeated measures, providing consistent estimates of regression coefficients and robust variance estimates, even in the presence of unbalanced group data. It permits the clustering of sites by treatment condition and provides a direct estimate of the ICC.

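### The primary GEE test on 16 sites in 8 matched pairs names no small-sample correction, reference distribution or pair term; in plain form the one-tailed .05 test runs at about 7–9.5% if paired sites are uncorrelated

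*Combined protocol and SAP*

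**What the plan says.** The Primary Outcome section sets the hypothesis that "the proportion in Action/Maintenance for the four ACP behaviors is intervention group > control group at the final 6-month assessment". It notes that "Several analytical approaches are available within a more general framework of random effects" modelling, and then settles the main method: "The basic analytical approach will employ the generalized estimating equation (GEE) method to analyze intervention main effects and interaction (additive) effects". It credits GEE with "providing consistent estimates of regression coefficients and robust variance estimates, even in the presence of unbalanced group data" and adds that "It permits the clustering of sites by treatment condition and provides a direct estimate of the ICC".

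The Power and Sample Size section counts 16 sites in 8 matched pairs, with 50 participants per site at the end. On the level it says: "Sample size calculations assumed one-tailed significance testing at alpha = .05". The Analysis section places sites within groups and says that randomisation was by matched pair. It names no pair effect in the model.

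No section gives a small-sample correction, degrees of freedom, a reference distribution, a permutation test, an ICC or a within-pair correlation.

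**The concern.** The sandwich variance is justified by a large number of independent clusters, and here there are 8 per arm. The usual estimator divides by the number of clusters rather than by one fewer in each arm, so it is too small on average. It is also noisy, and a normal reference ignores that. Both faults make the test liberal.

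Matching works the other way. If paired sites resemble each other, the arm difference varies less than an analysis without a pair term assumes, and the test is pulled back towards conservatism. The same written plan can therefore give a primary test that is too liberal, about right, or (corrected but ignoring pairs) too conservative. Which one depends on how GEE is run and on how well matching worked, and the plan fixes neither. A choice that moves the error rate of the primary test should not be left until the data are in hand.

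**Working it through.** **1. The plan's own sample size.** Inputs from Power and Sample Size: 5% v 15%, one-tailed .05, power .80, 16 × 50 = 800, 20% loss.

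- Loss to follow-up: 800 / (1 − .20) = 1000, as stated.
- Arcsine effect: h = 2·asin(√.15) − 2·asin(√.05) = .344.
- Without clustering, n per arm = 2·((1.645 + .842)/.344)² ≈ 104.3, so 400 per arm allows a design effect of 400/104.3 = 3.84.
- Setting 1 + 49·ICC = 3.84 gives ICC ≈ .058 with a normal reference. With t(14) it is about .050, and with t(7) about .043.

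The ICC is not stated, so the sample size can only be back-solved. It is plausible at an ICC of roughly .04–.06.

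**2. Closed form for the plain test.** With m = 8 sites per arm, the uncorrected variance is (m−1)/m of the unbiased one. One-tailed error ≈ P(t₁₄ > 1.645·√(7/8)) = P(t₁₄ > 1.539) = 7.3%. If observed site proportions correlate r within pairs, the threshold is divided by √(1−r), approximately:

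| r | 0 | .1 | .2 | .3 |
|---|---|---|---|---|
| Error | 7.3% | 6.4% | 5.4% | 4.4% |

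**3. Simulation of the plain test.** Assumed, because the documents give no values: beta-binomial sites, ICC .01–.05, null rate 5% or 10%, 16 sites averaging 50, site-size CV 0 or .5. The model is a logistic GEE with arm only, at month 6, clustered on site, with 20,000 replicates per scenario (Monte Carlo SE about .2 points).

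| Observed site-proportion correlation | One-tailed error |
|---|---|
| 0 | 7.5–9.5% (7.5–9.2% with exchangeable working correlation) |
| about .1 | 6.2–8.4% |
| about .2 | 5.4–7.6% |
| about .3 | 4.5–6.8% |

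A separate set of runs (100,000 replicates per setting, site-size CV 0 or .4) with uncorrelated pairs gave 7.3–7.5% at ICC .001–.01, 7.6–8.2% at .03, 7.9–8.7% at .05 and 8.4–9.9% at .10.

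**4. Which correlation is meant.** The table uses the correlation of observed site proportions. The reliability of a site proportion is 50·ICC/(1 + 49·ICC): .5/1.49 = .34 at ICC .01, 1.5/2.47 = .61 at .03, and 2.5/3.45 = .72 at .05. A correlation of .3 between true site effects is therefore only about .10, .18 and .22 between observed proportions. Simulated at a true-effect correlation of .3, for ICC up to .05, the error was 5.8–7.5% in one set of runs and 6.0–8.2% in another, so about 6–8%.

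**5. Repeated occasions.** Baseline carries no information on this outcome ("which, because of our exclusion criteria, will be 0% at baseline") and has no logit, so months 2, 4 and 6 were modelled. One-tailed error was 7.0–9.4% with uncorrelated pairs and 4.2–6.8% at an observed correlation near .3. The repeated-measures structure does not remove the problem.

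**6. More sites.** If the senior communities in Participants and Recruitment are additional pairs, with pairs uncorrelated: 24 sites give 6.5% in closed form and 6.0–7.4% simulated; 32 sites give 6.1% and 6.2–6.9%.

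**7. Alternatives on 16 sites, one-tailed .05.**

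| Test | Error |
|---|---|
| Paired t on site proportions, 7 df | 4.4–5.1% in all 48 scenarios |
| Within-pair permutation, 2⁸ = 256 assignments | 2.9–4.9% |
| Mancl-DeRouen sandwich, t(14) | 4.0–5.2% uncorrelated; 2.1–3.3% near observed .3 |

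**The case against.** Several points against the concern have force.

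- **The plain test is not mandated.** The section says that several approaches are available, and a competent analyst might add a correction. This stands, and it is why a reader should not infer that the trial's error rate will certainly be inflated. It does not help the plan, since the choice is left open.
- **Matching may repair the error.** If observed site proportions correlate near .3, the range straddles 5%. At ICC .01, however, reaching an observed .25–.30 needs a true-effect correlation of about .75–.89, which is near-perfect matching. The documents give no basis for assuming it.
- **Sidedness.** A reader might infer that the side of the test is missing altogether. The documents do not support that: the power section states one-tailed .05 and the primary hypothesis is directional. All that is missing is confirmation of that level in the analysis section.
- **Covariates.** The plan intends covariates in the outcome models, partly to reduce within-group dependency. Adjusted models were not simulated, so the percentages describe the unadjusted analysis only. This limitation stands.
- **Number of sites.** Participants and Recruitment can be read as adding matched communities to eight pairs of practices. With 24–32 sites the inflation shrinks to about 6–7.4% but does not vanish.
- **Cost.** At ICC .05 with uncorrelated pairs, every corrected option falls below the planned power. This stands and should be disclosed. The plain test's higher power is partly bought by its inflated error.

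**Conclusion.** The concern holds as an uncontrolled error rate in the primary test. GEE with robust variance on 16 sites in 8 matched pairs is specified without a small-sample correction, a reference distribution or a pair term. Run in its ordinary, unadjusted form at month 6, the one-tailed .05 test has a true error of about 7–9.5% if paired sites are uncorrelated. The error is about 6–8% if true site effects correlate .3 within pairs, and about 4–7% if observed site proportions correlate about .3.

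These ranges rest on assumed ICC .01–.05, null rate 5–10% and, in the main runs, site-size CV 0–.5. Inflation is clear only where matching adds little, and the documents do not show which case applies.

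**What to change.** Name one primary test before analysis, and use the same method for the confidence interval.

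- **Keep GEE clustered on site**, with a small-sample-corrected sandwich (for example Mancl-DeRouen) and a t reference on 16 − 2 = 14 df. It is conservative if pairs correlate.
- **Or use a pair-respecting site-level test**: a paired t on 7 df, or the within-pair permutation test. State that this estimates an equally weighted mean of site risk differences, which is not the effect that a participant-level logistic GEE estimates. It replaces GEE as the primary test, drops the repeated-measures structure, and needs a two-stage step to use individual covariates.

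Confirm in the analysis section the one-tailed .05 level used for the sample size, and state the final number of sites and pairs.

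The text change is a few sentences. The real cost is power, which should be restated for the chosen test with its assumed ICC. Simulated one-tailed power for 5% v 15%, 16 × 50, uncorrelated pairs:

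| Assumed ICC | Plain z | Mancl-DeRouen t(14) | Paired t(7) | Permutation |
|---|---|---|---|---|
| .05 | 85% | 75% | 77% | 74% |
| .03 | 93% | 86% | 88% | 85% |

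If matching works, the paired tests recover some of this. At ICC .05 and an observed pair correlation of about .18, power is 84% for the paired t, 82% for permutation and 77% for Mancl-DeRouen.

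### The plan expects 20% loss to follow-up, but its unweighted GEE is generally biased if that loss depends on earlier ACP progress differently by arm; month-2 and month-4 data could reduce this

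*Combined protocol and SAP*

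**What the plan says.** - **Expected loss** (Power and Sample Size): "a final sample size of 50 individuals per site is needed, resulting in a final study sample size of 800", and then "Assuming 20% loss to follow-up, a baseline sample size of 1000 is required". Inflating enrolment is the only provision for loss.
- **Primary method** (Primary Outcome): the hypothesis concerns the proportion in action or maintenance on all four behaviours at month 6. The basic approach is GEE, credited with "providing consistent estimates of regression coefficients and robust variance estimates, even in the presence of unbalanced group data".
- **Data structure** (Analysis): the design is "two groups (intervention, control) X four occasions (baseline, 2, 4, 6 months", with sites nested in groups. Primary Outcome also refers to repeated measures and to time and site effects.
- **Data available** (Description of Intervention Group; Description of Control Group): both arms are assessed at baseline and at 2, 4 and 6 months. The assessments cover stages of change, decisional balance and values/beliefs.

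The document states no missing-data assumption, weighting, imputation or sensitivity analysis. It also does not say how month-2 and month-4 data enter the primary model.

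**The concern.** Enrolling 1000 protects power, not validity. GEE tolerates unequal numbers of observations. Without weighting, however, it generally needs loss to be unrelated to outcome given the covariates in the model.

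It is plausible that loss here relates to outcome differently by arm. Only intervention participants receive feedback comparing their current with their prior responses. Controls answer the same questions without feedback, masked among other health behaviours. Participants who are not progressing might leave, or those who have finished might see no reason to continue.

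The expected control rate is 5%, so the planned loss of 20% is four times that rate, and modest differences in who is lost can shift the result. Equal overall loss in the two arms does not prevent this.

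**Working it through.** **Inputs from Power and Sample Size.** 16 sites in 8 pairs; 50 analysed per site; 20% loss; one-tailed alpha .05; power .80; month-6 control rate 5%; difference 10 points, so 15% in the intervention arm. The loss patterns below are assumptions.

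**1. The plan's own figure.** 16 × 50 = 800 and 800/(1 − 0.20) = 1000, as stated. No ICC is given, so the 800 cannot be derived independently. With the arcsine effect size h = 0.344 for 15% vs 5%, 400 per arm and a t reference on 14 df, power of .80 implies an ICC of about .0503 (design effect 1 + 49 × .0503 = 3.46). That value is used in step 4.

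**2. Month-6 complete cases, true 15% vs 5%.** With 20% loss in an arm, observed rate = p × (1 − loss among achievers)/0.80. Control loss is random, except in the last row.

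| Loss among achievers | Intervention | Control | Difference | Bias |
|---|---|---|---|---|
| Intervention 0% | .15 × 1.0/.80 = 18.75% | 5.0% | 13.75 | +3.75 |
| Intervention 10% | .15 × .90/.80 = 16.9% | 5.0% | 11.9 | +1.9 |
| Intervention 30% | .15 × .70/.80 = 13.1% | 5.0% | 8.1 | −1.9 |
| Both arms 10% | 16.9% | .05 × .90/.80 = 5.6% | 11.25 | +1.25 |

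In the last row the odds ratio is 3.41 against a true 3.35, so it is almost unbiased although the risk difference is not.

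**3. Using months 2 and 4 as outcomes.** Three patterns of loss depending on month-4 progress were simulated, with about 20% loss per arm and a true difference of about 10 points. Bias in points:

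| Pattern | Complete case | Exchangeable GEE, months 2, 4, 6 | Weighted on arm and month-4 progress |
|---|---|---|---|
| 1 | +1.4 | +0.6 | within 0.1 |
| 2 (intervention arm only) | +2.4 | +1.2 | within 0.1 |
| 3 | +3.1 | +1.2 | within 0.1 |

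The upward sign follows from the assumed patterns and is not evidence of direction. Weighting does well here because loss was made to depend on month-4 progress, which is observed.

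**4. False-positive rate, complete cases.** Assume half of each arm progresses by month 4, with month-6 success of 10% in progressors and 0% in the rest, so the truth is 5% vs 5%. Control loses 20% at random. Intervention loss is 20% overall, split between progressors and the rest:

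- 5% and 35%: .5 × .95 × .10/.80 = 5.94%; one-tailed error .089.
- 12.5% and 27.5%: .5 × .875 × .10/.80 = 5.47%; error .068.
- 35% and 5%: .5 × .65 × .10/.80 = 4.06%; error .024.

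**5. Lost counted as non-completers.** If 60/400 vs 20/400 are observed, this gives 60/500 = 12% vs 20/500 = 4%, or 8 points instead of 10. The 12% and 4% correspond to a true 15% and 5% with random loss; other loss patterns give other figures.

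**The case against.** **The analysis is not confined to month 6.** A reader might infer that the GEE uses month-6 data alone and that the interim stages are ignored. The document does not say so: Analysis sets out four occasions and Primary Outcome refers to repeated measures. This stands, and the complete-case figures describe only one permitted reading. On the other reading, step 3 still leaves +0.6 to +1.2 points. The primary composite is also 0% for everyone at baseline by design, and as a yes/no variable it records no partial progress. The component stages therefore hold information that a GEE on the composite does not use.

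**The sentence on unbalanced data is a general description of GEE.** It can be read as referring to unequal group or site sizes and makes no claim about informative loss. This also stands. The weakness is that nothing else in the plan addresses such loss.

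**Covariates and symmetry help.** It would be too strict to say that the analysis is unbiased only if loss is unrelated to ACP progress. Loss explained by covariates in the model is tolerated, and loss related to outcome in the same way in both arms leaves the odds ratio nearly unchanged. However, the target effect is stated as an absolute difference, which does change.

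**The mechanism is conjecture.** Nothing in the document says that non-progressors leave, and Outcome Measures describes materials that avoid pressing participants to act. A reader might infer an inflated effect and too many false positives. The document does not support a direction: the mirror pattern makes the test conservative (.024), and the 5%/35% split is extreme.

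**Conclusion.** The concern holds in limited form. The plan expects 20% loss and names a method that is generally not consistent if loss depends on earlier ACP progress differently by arm, while scheduling in both arms the data that could reduce the problem.

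Neither the size nor the direction of bias can be known in advance. The ranges shown rest on assumed loss patterns, and the error rates also on an ICC of about .05 that the document does not state. Those error rates apply to month-6 complete cases; the simulations suggest less distortion where months 2 and 4 enter as outcomes. The point bears on how far the result can be trusted. It does not show that the trial will overstate its effect.

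**What to change.** 1. State the missing-data assumption and make the primary month-6 analysis include all enrolled participants.
2. Multiply impute month-6 stage for each behaviour, separately by arm and respecting site. Use as predictors the baseline, month-2 and month-4 stages, decisional balance, values/beliefs and the baseline covariates. Inverse-probability-weighted GEE with the same predictors is an acceptable alternative.
3. Use the month-2 and month-4 data only as predictors, because blinding is stated only for the month-6 interviewer.
4. Add two sensitivity analyses: lost participants counted as not in action or maintenance, and an arm-specific shift in the imputed odds of success. They are needed because step 2 cannot correct loss driven by unseen month-6 status and has only baseline data for people lost before month 2.

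The cost is additional analysis and programming. No new data are needed and the sample size stays at 1000.

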### **Secondary Outcomes**

Design and analysis approaches for secondary outcomes will be similar to those employed for the primary outcome variable. Subgroup analysis will explore the effects of the intervention according to demographic status, including age, gender, race/ethnicity, education, and according to the number of ACP behaviors completed at baseline.
